11 SITE MONITORING PLAN

Site monitoring will be conducted to ensure that human subject protection, study procedures, laboratory procedures, study intervention administration, and data collection processes are of high quality and meet sponsor, GCP/ICH, and regulatory guidelines, and that the study is conducted in accordance with the protocol and sponsor standard operating procedures. DMID, the sponsoring agency, or its designee will conduct site-monitoring visits as detailed in the monitoring plan.

Site visits will be made at standard intervals as defined by DMID and may be made more frequently as directed by DMID. Monitoring visits will include, but are not limited to, review of regulatory files, accountability records, CRFs, informed consent forms, medical and laboratory reports, source documents, data collection forms, medical records and protocol compliance. Study monitors will meet with investigators to discuss any problems and actions to be taken and document visit findings and discussions.

12 STATISTICAL CONSIDERATIONS

12.1 Sample size calculations

The primary endpoint is the incidence of CMV disease within 12 months post transplantation. The null hypothesis is that the incidence of CMV disease in the prophylaxis group is equal to that in the preemptive therapy group. The null hypothesis will be rejected if there is a significant difference between the two groups at 0.05. The sample size estimates have been calculated based on the numbers required to detect a disparity in two survivor functions using a two-sided log-rank test [stpower logrank, STATA version 10.1]. The calculations are based on a realistic and conservative expectation in differences in event (CMV disease), feasibility and clinically relevant effect size. The mean CMV disease rate (weighted for study size) for prophylaxis and preemptive therapy studies (depicted in the Tables in the Background section of the protocol) is 30.6% (95% CI 24.1-37.1) and 0.78% (95% CI: 0-2.4%), respectively. Based on power calculations that coincide with the lowest observed rate for CMV disease in prophylaxis studies and highest rate observed in preemptive therapy studies, we assume that CMV disease will occur in 20% of the subjects in the prophylaxis and 5% in the preemptive therapy group. A sample size of 160 study subjects (80 per group) will detect this difference with power of 80% and alpha =0.05 using two-sided Fisher's exact test for two independent proportions. The Table below provides sample size estimates for CMV disease rates of 20-25% in the prophylaxis and 5-7% in the preemptive therapy group.

Prophylaxis group		Preemptive therapy group		Hazard ratio	Power	Estimated events	Sample size each group	Total sample
Estimated disease rate	Disease free survival	Estimated disease rate	Disease free survival					
25%	.75	7.1%	.929	.254	.83	25	75	150
25%	.75	7.1%	.929	.257	.85	26	80	160
22%	.78	7.0%	.930	.291	.80	27	90	180
20%	.80	5.0%	.950	.229	.80	20	80	160
20%	.80	6.0%	.941	.273	.80	25	93	186
20%	.80	5.4%	.946	.247	.80	22	85	170
20%	.80	7.0%	.930	.325	.80	31	112	224

Non-inferiority: Although the study sample size is powered to detect the superiority of one preventive strategy compared to the other, it is possible that the two approaches may be similar in efficacy with respect to CMV disease. Therefore a non-inferiority assessment will be done using a non-inferiority margin of 5%. This margin is based on what is known about the effectiveness of the two approaches in the literature and the potential that the two strategies may be equally efficacious in preventing CMV disease. As noted above, the success rate for the prophylaxis group is estimated at 75 to 80% based on previous studies with comparable success rates for the preemptive group. The null hypothesis for non-inferiority is that the success rate (percent of subjects remaining CMV disease free) for subjects in the prophylaxis group is better than the success rate for those in preemptive therapy group by 5%. The null hypothesis will be rejected and the preemptive therapy will be considered to be non-inferior if the success rate in the prophylaxis group is less than 5% greater than that in the preemptive therapy group. Sample size estimates for non-inferiority are given below at alpha=.05

Success in prophylaxis group	Success in preemptive therapy group	Non inferiority margin	Sample size each group [total sample]	Power
80%	85%	10%	80 [160]	80
80%	85%	8%	106 [212]	80
80%	90%	5%	96 [192]	90
80%	90%	5%	70 [140]	80
80%	89%	5%	80 [160]	80
80%	85%	5%	178 [356]	80
75%	85%	5%	87 [174]	80
75%	90%	5%	76 [152]	95
75%	90%	2%	83 [166]	90
75%	88%	5%	78 [156]	90
80%	80%	5%	792 [1584]	80

Note: for "equivalence" at 80% success rate in each group and a 5% equivalence limit, a sample of 1097 in each group would be required [2194 total subjects] at alpha=.05 and power=.80.

Our sample size is adequate to assess both superiority and non-inferiority (with a margin of 5%) without statistical penalty. In a sample size of 160 subjects, if there is a true difference of 9% in favor of the preemptive therapy group [9% higher success rate for CMV disease prevention]; we can be certain (with power equal to 80%) that the upper limit of a one-side 95% confidence interval will not include a difference of more than 5% (non-inferiority margin) in favor of the prophylaxis group.

12.2 Treatment groups

Subjects will be randomized into one of the two groups in 1:1 ratio. Prophylaxis group will receive VGCV for 100 days and preemptive therapy group will undergo weekly CMV PCR screenings and receipt of VGCV following a positive CMV PCR test. A stratified, blocked randomization scheme will be utilized in order to keep the sample sizes similar in both groups.

Subjects at each site will be stratified by receipt of anti-lymphocyte induction therapy and renal dialysis at the time of randomization. Subjects will be consecutively entered.

12.3 Populations for analysis

There will be two analysis populations: Intent-to-treat (ITT) and a modified ITT. Limited summary information will be provided for screen failures. An ITT analysis will be conducted for the primary endpoint.

12.3.1 Intent-to-treat (ITT) population

All subjects who meet all eligibility criteria, sign an informed consent form, and are randomized to one of the treatment groups constitute the ITT population regardless of whether they received valganciclovir or had any post-baseline evaluations.

12.3.2 Modified intent-to-treat population

The modified ITT population will consist of those subjects in ITT population who were randomized and received at least one dose of valganciclovir in the prophylaxis group or had at least one CMV PCR test post-randomization in the preemptive therapy group.

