The other drug that was carefully considered but ultimately rejected was oral ganciclovir. The key argument against its use is its poor oral bioavailability and the consideration that the most active available anti-CMV agent should be used in the preemptive therapy arm since these subjects will have viremia. It is proposed that in a CMV-naïve host, an anti-CMV drug must be \geq 93.3% effective to fully inhibit viral growth; the estimated efficacy of iv ganciclovir (5 mg/kg bid) for inhibition of viral growth is \sim 91.5% and that of oral ganciclovir is only \sim 46.5% (50). Use of oral ganciclovir in the prophylaxis group was also rejected, the rationale being concerns for low bioavailability, large pill burden, and data suggesting that it is associated with a higher incidence of resistance compared to valganciclovir (51). Additionally, as of May 2009, oral ganciclovir is unavailable from the manufacturer (Ranbaxy) due to issues related to acquisition of raw materials.

The usual dosage of valganciclovir when used for prophylaxis is 900 mg orally daily. For preemptive therapy, a 900 mg bid dose is used (21, 24). The rationale for the dose in this group is that CMV infection (viremia) would already have occurred and therefore the purpose of antiviral therapy is to prevent the progression of asymptomatic infection to CMV disease. Indeed, preemptive therapy is often termed "early treatment" strategy for the aforementioned reason. Since the dose of valganciclovir that achieves blood levels equivalent to 5 mg/kg bid of iv ganciclovir (or the treatment dose for CMV) is 900 mg po bid (52), the drug dosage utilized for preemptive therapy will be 900 mg bid.

If a subject is unable to tolerate oral medications, intravenous ganciclovir may be substituted for oral valganciclovir because the study intends to compare the approach to prevention of CMV and not a particular formulation of ganciclovir. Since drug levels achievable with valganciclovir are similar to that with intravenous ganciclovir, brief substitution with the

latter agent is unlikely to confound any of the end-points and will prevent unnecessary discontinuation of the drug and exclusion of subjects.

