6 STUDY INTERVENTION/INVESTIGATIONAL PRODUCT

6.1 Study Product Acquisition/Description

Valganciclovir is the standard of care for CMV prevention at all participating centers. Valganciclovir will be used on an open-label clinical basis and billed to the subject and/or insurer. The subjects may fill prescription at any pharmacy per standard clinical care at that institution. No medication will be provided specifically for study purposes.

Valcyte ® (valganciclovir HCl tablets) is available as 450 mg pink convex oval tablets with "VGC" on one side and "450" on the other side. Each tablet contains valganciclovir HCl equivalent to 450 mg valganciclovir. The dispensing of valganciclovir will be according to manufacturer recommendations and routine institutional practices at the transplant center.

It is possible that a generic formulation of valganciclovir might be approved and become available during the study period. Investigators may use either formulation of valganciclovir (brand vs. generic equivalent) for study subjects at the protocol-described doses according to institutional standards. Because of the uncertainty of if/when generic valganciclovir might become available; it will not be possible to specifically control for this variable in the pre-defined analytic plan. However, we will include post-hoc analyses to assess the potential impact of generic formulations of valganciclovir on the study safety and efficacy endpoints.

For this protocol, all references to "study drug" are referring to valganciclovir when prescribed per Section 6.2, and beginning with Study Day 1. "Study drug" includes dose adjustment when indicated and the use of ganciclovir when indicated per clinical care.

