6.2.3 Conditions limiting valganciclovir administration

Subjects in either group who are unable to take valganciclovir orally at any time during the study period may receive IV ganciclovir until oral valganciclovir can be resumed. Subjects in either group may also be switched to IV ganciclovir if conditions that preclude use of oral valganciclovir develop such as inability to take oral medications or reduction in CrCl to < 10 ml/min or requirement for dialysis. These subjects may remain on IV ganciclovir until valganciclovir can be resumed. For handling of interruptions of valganciclovir due to neutropenia please see section 7.6.2.

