12.4.5 Duration of treatment, compliance, and participation

Duration of valganciclovir, length of study participation (while on therapy and during follow up), compliance as well as a distribution of the number of days from the date of transplantation to the date of the first dose of valganciclovir [prophylaxis arm] or date of first CMV PCR test [preemptive arm] will be summarized for the modified ITT population using descriptive statistics, including frequency distributions. For the preemptive arm the number of PCR tests, number of days between positive PCR test and the initiation of valganciclovir as well as the exposure to valganciclovir will be summarized.

Duration of valganciclovir is (date of the last dose of drug minus the date of first dose of drug plus 1 day).

Study participation as defined by the duration of the overall CMV evaluation period (while on therapy and during follow-up) will be summarized for the ITT and modified ITT populations. Evaluation period length for CMV disease assessment is (date of last study contact minus the date of randomization plus 1 day).

Receipt and duration of generic or nongeneric valganciclovir will be recorded and summarized for each study population.

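### The modified ITT entry rule for the prophylaxis arm counts only valganciclovir, although IV ganciclovir is study drug, and sections 12.3.2 and 12.5.5 define the population differently

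*Combined protocol and SAP*

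**What the plan says.** **Entry rule.** Section 12.3.2 requires that a prophylaxis subject "received at least one dose of valganciclovir in the prophylaxis group", or that a preemptive subject "had at least one CMV PCR test post-randomization in the preemptive therapy group". The first condition names one drug. The second does not depend on drug at all.

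**Study drug.** Section 6.1 defines the term for the whole protocol and states that it "includes dose adjustment when indicated and the use of ganciclovir when indicated per clinical care".

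**Permitted substitution.** Under section 6.2.3, subjects in either group who cannot take the oral drug "may receive IV ganciclovir until oral valganciclovir can be resumed". The listed triggers are "inability to take oral medications or reduction in CrCl to < 10 ml/min or requirement for dialysis". No time limit is set: "These subjects may remain on IV ganciclovir until valganciclovir can be resumed". The footnote in 6.3 leaves practice in hemodialysis to the sites, and 6.5 repeats the permission for IV ganciclovir.

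**Intent.** Section 2.2.2 explains the substitution by saying that "the study intends to compare the approach to prevention of CMV and not a particular formulation of ganciclovir". It adds that allowing the substitution avoids excluding subjects needlessly.

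**Second definition.** The bracketed text in 12.5.5 describes the modified ITT again. There the drug condition is tied to withdrawal before valganciclovir and is attached to the preemptive arm, next to the condition on PCR testing. No condition is stated for the prophylaxis arm.

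**Descriptive summary.** For the prophylaxis arm, section 12.4.5 measures the interval from transplantation to the first valganciclovir dose.

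**The concern.** The modified ITT population is meant to hold subjects who started their assigned strategy. For a prophylaxis subject started on IV ganciclovir, 12.3.2 uses a narrower test than the protocol's own definition of study drug. The same subject counts as treated under the replacement rule (5.4.2 and 5.4.3.3, which turn on receipt of study drug) and as untreated for the modified ITT.

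The exclusion would be made after randomization and on the basis of route, which the trial says it is not comparing. It reaches these analyses:

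- the modified ITT repeat of the primary analysis (12.5.5)
- the infection incidence test (12.6.1.3), neutropenia (12.6.2.1) and growth factor use (12.7.2.1), where the modified ITT is the population named

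Because 12.3.2 and 12.5.5 disagree, two analysts following the plan could also build different populations.

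**Working it through.** The plan gives no figure to reproduce on this point. The check compares the two definitions case by case and then sizes the effect under stated assumptions.

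**1. The two definitions, read literally**

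| Subject | 12.3.2 | 12.5.5 |
|---|---|---|
| Prophylaxis, IV ganciclovir from day 1, dies before any oral dose | out | in |
| Prophylaxis, IV ganciclovir, later at least one valganciclovir dose | in | in |
| Prophylaxis, no antiviral dose, withdraws | out | in |
| Preemptive, at least one PCR, never needs drug, withdraws | in | out |
| Preemptive, at least one PCR, IV ganciclovir only, stays in the study | in | in |
| Preemptive, dies before the first PCR | out | out |

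The first row is the gap in the entry rule. Rows one, three and four show the conflict between the sections. In row four, 12.5.5 would remove a preemptive subject who was managed exactly as assigned, which suggests that the arm label there is a slip.

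**2. Who can fall in the first row**

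One valganciclovir dose at any time satisfies 12.3.2, so the gap concerns subjects who never have one. Randomization takes place within 10 days of transplant, and among the very sick only a life expectancy under 72 hours excludes (5.3). A subject unable to take oral drug who dies or withdraws before any oral dose is therefore possible. Dialysis at randomization is a stratum (5.4.2), but section 2.2.2 says that all sites already use valganciclovir in dialyzed patients, so few IV-only subjects should arise by that route. Section 12.3.2 also does not say that the dose must follow randomization. Since 5.4.2 permits earlier valganciclovir, a dose given before randomization might admit a subject.

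**3. Size, under assumptions**

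Inputs: n = 176 / 2 = 88 per arm (minimum enrollment in section 4); event rate 20% in the full prophylaxis arm (the CMV disease rate assumed in 12.1, used here as a generic rate). Assumed, because the plan gives neither: k = 1 to 8 IV-only prophylaxis subjects, with event risk q = 0 or 0.5 among them.

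Rate after exclusion = (88 × 0.20 − k × q) / (88 − k) = (17.6 − kq) / (88 − k)

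| k | share of arm | q = 0 | shift (points) | q = 0.5 | shift (points) |
|---|---|---|---|---|---|
| 1 | 1.1% | 17.6/87 = 20.2% | +0.2 | 17.1/87 = 19.7% | −0.3 |
| 3 | 3.4% | 17.6/85 = 20.7% | +0.7 | 16.1/85 = 18.9% | −1.1 |
| 5 | 5.7% | 17.6/83 = 21.2% | +1.2 | 15.1/83 = 18.2% | −1.8 |
| 8 | 9.1% | 17.6/80 = 22.0% | +2.0 | 13.6/80 = 17.0% | −3.0 |

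If the excluded subjects have the arm's own risk (q = 0.20), the shift is zero. The sign depends entirely on q.

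**4. Descriptive summary**

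Under 12.4.5, a prophylaxis subject on IV ganciclovir from day 1 who later changes to the oral drug is dated from the change, and so appears as a late starter. The duration formula speaks of drug in general but sits under a label that names valganciclovir.

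**The case against.** The strongest reply is that this is loose wording with little effect. Section 6.1 shows that ganciclovir was meant to count, and 2.2.2 expects only brief substitution. The primary analysis is ITT (12.3 and 12.5.4), and infection rates are also compared in the ITT population, though as an exploratory analysis (12.7.1.7). The item in 12.4.5 is descriptive, with no test attached. All of this stands as a limit on importance. It does not cure the rule, because 12.3.2 uses the drug's name and not the defined term.

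A reader might go further and infer that the rule removes the sickest subjects from the prophylaxis arm alone, and so flatters prophylaxis on infection and neutropenia. The documents do not support that, for three reasons.

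- **Not one arm alone.** Preemptive PCR testing starts on study day 7, with a window of 3 days either side (7.5.2 and 7.5.3.2). A preemptive subject who dies or leaves before the first PCR is excluded too, whereas a prophylaxis subject normally qualifies on day 1. For early deaths the rule can remove very sick subjects from the preemptive arm, so the net imbalance is unknown.
- **Infection.** Sicker subjects may have a higher risk, but those who die or withdraw early have little time in which an infection can be recorded. The sign could go either way.
- **Neutropenia.** Section 2.3.1.2.6 puts onset at a median of 5 weeks after exposure and cites 0% at day 21 on IV ganciclovir. Early leavers would add few events, so dropping them would, if anything, raise the prophylaxis rate.

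**Conclusion.** The point holds as a defect of definition. Followed literally, 12.3.2 excludes prophylaxis subjects who received their assigned strategy only as IV ganciclovir, against the study drug definition in 6.1 and the intent stated in 2.2.2. Section 12.5.5 gives a second definition that conflicts with it.

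The number affected is not given and is probably small: mainly subjects unable to take oral drug who die or withdraw before any oral dose. The shifts above, from +2.0 to −3.0 points at most, rest on assumed counts and risks and show only that either sign is possible. No direction of bias is established. The primary ITT result is unaffected. The change should be made before analysis because the infection, neutropenia and growth factor comparisons are exposed and membership of the population should not be left to interpretation.

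**What to change.** - **12.3.2:** replace the valganciclovir condition for the prophylaxis arm with *at least one dose of study drug as defined in section 6.1 (valganciclovir or IV ganciclovir) on or after study day 1*. This also settles the status of doses given before randomization, and it agrees with 6.2.2.1, which counts a standard-care dose on study day 1 as the first study dose.
- **12.5.5:** rewrite the bracketed exclusion to match 12.3.2, with the drug condition applied to the prophylaxis arm and the PCR condition to the preemptive arm. Swapping the drug term alone would not work, because the exclusion there is built on withdrawal and names the other arm.
- **12.4.5:** count time to first dose and duration from the first dose of either drug.

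The cost is a change of wording in the analysis plan. Baseline antiviral doses (8.1.1) and antiviral treatment during the study (8.1.5) are already collected. The only check needed is that the case report form holds the start date of IV ganciclovir. No treatment rule, visit or sample size changes.

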12.3.3 Screen failures

Subjects that were screen failures will be summarized as to the reason for screen failure with no further characterization. Screen failures will include patients that never signed consent as well as those that signed consent but did not meet eligibility criteria and therefore were never randomized

12.4 Data Analyses

12.4.1 General considerations

All statistical analyses will be performed using STATA version 10.1 or later [Stata Corp, College Station, TX] or SAS version 9.2 or later [SAS Institute Inc., Cary, NC]. Cost efficacy analysis will use TreeAge Pro 2011 or later [TreeAge software, Williamstown, MA]. Tests of statistical significance will be two sided at an alpha of 0.05 unless otherwise specified.

12.4.2 Missing data

Sensitivity analysis employing imputation of missing values will be carried out for efficacy and safety endpoints as appropriate. The type of imputation is specified under the analysis section for each end point where imputation is employed. In addition, imputation will be employed for missing or incomplete dates for the onset of adverse events. For selected analyses, a complete date is necessary to determine whether or not an adverse event began after study treatment. In cases where an incomplete onset date is provided in the case report form (CRF), the missing components will be defined as follows:

- Missing day, month and year present: If month and year are the same as the first treatment dose month and year, the day will be assumed to be the same as the first dose day. Otherwise, the day will be assumed to be the 15th.
- Missing day, month and year: The date will be assumed to be the same as the first treatment dose date. If the imputed date is after the resolution date, the imputed onset date will be assumed to be the same as the resolution date.
- Severity and causality of adverse events occurring on or after the start of study drug are imputed when missing events for which causality was unknown or not recorded will be included in the summary of study drug related events.

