6.2.2.1 Prophylaxis group

Subjects assigned to the prophylaxis arm will receive valganciclovir at a dose of 900 mg po qd (adjusted for renal dysfunction). Study drug will be given on the day of randomization (considered Day 1 of the study) and will be administered for 100 days.

For subjects randomized to the prophylaxis group that have been receiving prophylaxis therapy for CMV as part of their standard care prior to randomization, the prophylaxis dose will not be repeated on study day 1 if a dose has already been administered. However, if a dose was given as standard care, the dose will be counted as the 1st day of the 100 days of study treatment doses.

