7.7.1 Study day 1-100

Drug administration phase

Prophylaxis therapy group will begin to receive antiviral prophylaxis treatment on day 1 and will continue receiving a daily dose through day 100. Please see protocol section 6.2 for a complete description and instructions regarding of prophylaxis dosing.

Preemptive treatment group will begin preemptive antiviral drug therapy during study days 1-100 only when viremia is detected by weekly surveillance and will continue preemptive therapy until two consecutive weekly CMV PCRs are negative. Therapy may be repeated if further detection of viremia is detected during the 100 day period.

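### Incomplete adverse event onset dates are imputed from the first valganciclovir dose, an anchor that equals study day 1 in the prophylaxis arm but comes later or never in the preemptive arm

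*Combined protocol and SAP*

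**What the plan says.** Section 12.4.2 of the combined protocol and SAP sets one rule for both arms.

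- Day missing, month and year equal to those of the first dose: "the day will be assumed to be the same as the first dose day".
- Day missing, any other month: "Otherwise, the day will be assumed to be the 15th".
- Day, month and year all missing: "The date will be assumed to be the same as the first treatment dose date". If that date is later than resolution, "the imputed onset date will be assumed to be the same as the resolution date". This cap is written only under this second bullet.
- Third bullet: for events on or after the start of study drug, missing severity and causality are imputed, and "events for which causality was unknown or not recorded will be included in the summary of study drug related events".

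The stated reason is that "a complete date is necessary to determine whether or not an adverse event began after study treatment".

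Section 6.2.2.1 starts prophylaxis on the day of randomization. Section 7.7.1 starts preemptive drug "only when viremia is detected by weekly surveillance". Weekly PCR begins on study day 7 (7.5.2) with a window of 3 days either side (7.5.3.2), and drug follows within a week of a positive result (6.2.2.2). All subjects are assessed for adverse events from study day 1 (7.7.4). Safety labs are recorded whether or not drug was given, and an ANC below 1000/µL is reported as an adverse event (7.5.3.1).

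**The concern.** In the prophylaxis arm, first dose and randomization are the same day. In the preemptive arm first dose can fall from about day 4 (a day 7 sample taken 3 days early, with drug started at once) to beyond day 100, or not at all. That arm therefore has a period under observation but off drug, and some of its subjects are never on drug.

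The same incomplete record is then handled differently by arm. The rule can place a preemptive event before randomization, move a pre-drug event onto drug, or fail to give a date. Because the third bullet depends on drug start, a pre-drug event moved onto drug with causality missing would be counted as drug related. Section 12.6.3 compares severe, unexpected drug-related events between the groups.

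Section 12.4.5 already handles this asymmetry in another summary: it uses first dose for prophylaxis and first PCR test for preemptive therapy. Section 12.4.2 does not.

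**Working it through.** The plan states no figure on this point, so there is none to reproduce.

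**Example.** A preemptive subject is randomized on 20 March, with first dose on 24 April.

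- Event 25 March, day missing: month differs from first dose, so 15 March, 5 days before randomization.
- Event 5 April, day missing: same month as first dose, so 24 April, on drug.
- Wholly missing, unresolved or resolved after 24 April: 24 April, on drug.
- Wholly missing, resolved 10 April: the cap gives 10 April, still pre-drug.
- Same subject never treated, wholly missing: no first dose, so no date. With March known, the event would get 15 March.

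**Size for a missing day.** Assumptions, since the documents give none: randomization spread evenly over the calendar, onset uniform by day, first dose on study day D. I applied the rule to every randomization date in 3.5 years; the short formulas below match the results.

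*Pre-drug events moved onto drug.* An event moves when it shares a calendar month with the later first dose. For D up to 28 the mean gap between event and dose is D/2 days, so the share is about 1 − (D/2)/30.4. At D = 14 this is 1 − 7/30.4 = 77%; at D = 28, 1 − 14/30.4 = 54%. For later doses, the first-dose month contains on average 14.7 earlier days, so the share is about 14.7/(D − 1): 14.7/41 = 36% at D = 42 and 14.7/83 = 18% at D = 84.

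*Events dated before randomization.* This needs randomization after the 15th and onset later in that month, with first dose in another month or absent. A month of L days contributes (L − 15)(L − 14)/2 such days. Over a year that is 7×136 + 4×120 + 91 = 1,523, or 1,523/365 = 4.17 days per subject. Over days 1-107 this is 4.17/107 = 3.9%. An early first dose in the same month lowers it.

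| First dose | Pre-drug events moved onto drug | Same, as share of all day-missing records, days 1-107 | Dated before randomization, share of all day-missing records |
|---|---|---|---|
| Day 14 | 77% | 9% | 2.8% |
| Day 28 | 54% | 14% | 3.9% |
| Day 42 | 36% | 14% | 3.9% |
| Day 84 | 18% | 14% | 3.9% |
| Never | not applicable | not applicable | 3.9% |
| Day 1 (prophylaxis) | not applicable | not applicable | 0% |

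At the extremes, the share moved is 93% for a first dose on day 4 (0.2% before randomization) and 14% on day 105.

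**Cap.** Read as placed, it does not cover a missing day. An event resolved on the 8th can then get onset on the 15th, in either arm. For onset spread evenly over the month and a duration of d days, this happens when onset falls before day 15 − d: 11/30.4 = 36% for 3-day events and 7/30.4 = 23% for 7-day events (durations assumed), among events dated to the 15th.

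**Randomization as anchor instead.** Dates before randomization fall to 0%. The share of pre-drug events moved onto drug falls from 77% to 20%, 54% to 13%, 36% to 8% and 18% to 4% for D = 14, 28, 42 and 84.

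**The case against.** The strongest reply is that little in the planned analysis uses these dates.

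- The main comparison in 12.6.3 counts reportable events per person-day, and neutropenia (12.6.2.1) comes from scheduled labs. This largely stands. A reader might infer that the between-arm adverse event comparison is biased as a whole; the documents do not support that. The exposed part is the drug-related comparison in the same section, through the third bullet of 12.4.2.
- Criterion 1 in 9.2.3 is worded for a subject receiving study drug, which may keep some pre-drug events out of the record. This stands as a limit, but it sits uneasily with assessment of all subjects from day 1 (7.7.4) and ANC reporting regardless of drug (7.5.3.1).
- Onset time is a required item (9.3) and missing data are queried (section 14), so incomplete dates should be uncommon. That is plausible, and the number is not given.
- Assigning doubtful events to drug is the cautious direction for safety. That is fair for one arm, but it does not justify dates before randomization or no date at all.
- Randomization as anchor brings the opposite error. This stands. It dates about 5% to 17% of true on-drug, day-missing events as pre-drug for first doses on days 14 to 84, where the current rule gives 0%. It also puts every wholly missing date in a treated preemptive subject before drug. The onset date and on-drug status therefore need separate rules.

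**Conclusion.** The point holds as a minor defect: a stated rule gives wrong or impossible dates, almost entirely in one arm. In the preemptive arm about 3-4% of day-missing records are dated before randomization, for a first dose on day 14 or later or none. Between 77% and 18% of pre-drug, day-missing events move onto drug for first doses on days 14 to 84. Both figures rest on uniform onset and assumed first-dose days. The absolute effect scales with the unknown number of incomplete dates.

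Three stronger readings go too far.

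- Never-treated subjects do not all lose their dates; only a wholly missing date fails.
- The documents do not say that first dose is always weeks after randomization. It can be as early as about day 4, and 12.4.2 does not say whether the antiviral given after lymphocyte-depleting induction (5.4.2) counts as a first treatment dose.
- The rule is not faultless in the prophylaxis arm, because the gap in the cap affects both arms.

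**What to change.** In 12.4.2, separate two things.

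1. **Onset date, both arms.** Anchor on randomization (study day 1). If month and year equal those of randomization, use the randomization date; for any other month use the 15th; if all parts are missing, use the randomization date. Apply the resolution-date cap to every case. No imputed date then precedes randomization and every subject has an anchor.
2. **On-drug status, preemptive arm.** Do not derive it from the imputed date. Where the known date parts leave the order relative to first dose open, classify the event as timing unknown. Report the on-drug and drug-related summaries twice, once with these events counted as on drug and once with them excluded. Events in never-treated subjects are off drug. State whether antiviral given after induction counts as the first treatment dose for this classification.

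The cost is a few sentences, a small change to the derivation and one extra sensitivity summary. No new data are needed.
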